1.5 Study Data

The study data includes all clinical data captured by eCRF and safety lab data. The eCRF database will be locked for the final analyses and the final data transfers from the central lab will be utilized. Biomarker data is considered exploratory and will not be included in the eCRF database.

The investigator must maintain adequate and accurate records to enable the conduct of the study to be fully documented and the study data to be subsequently verified. These documents should be classified into three separate categories (although not limited to) the following: (1) investigator's study file, (2) subject blinded clinical source documents, and (3) subject unblinded clinical source documents.

The investigator's study file will contain the protocol/amendments, CRF, IRB approval with correspondence, informed consents, drug records, staff curriculum vitae and authorization forms, and other appropriate documents and study-specific manuals (e.g., lab manual).

Subject clinical source documents would be separated according to blinded source and unblinded source and include (although are not limited to) the following: subject hospital/clinic records, physician's and nurse's notes, appointment book, original laboratory reports, ECG, radiologic imaging, X-ray, pathology and special assessment reports, consultant letters, screening and enrollment log, etc.

2 GENERAL ANALYSIS DEFINITIONS

All analysis dataset preparations and statistical analyses will be performed using SAS® version 9.4 or higher. No imputation will be performed for missing data unless stated otherwise. Listings for CSR Appendix 16.2 will include all the subject data points being collected or derived for analyses, and will be sorted by treatment group, site, and subject number.

2.1 Treatment Groups

[figure not shown]
The two treatment groups will be labelled as GRF6019 250 mL or placebo within the statistical output.

The treatment period includes a total of 5 infusions during Week 1. It is anticipated that sites will infuse subjects with 5 doses over 5 days. A “grace day” is allowed in the event of unanticipated safety or health concerns during the treatment period.

2.2 Statistical Hypothesis Tests

Because the primary objective of the study is safety and tolerability, it is not designed to detect statistically significant differences between active and placebo efficacy endpoints. The statistical approach toward secondary endpoints will be primarily descriptive; within-subject changes from baseline for each dosing group among-group differences will be evaluated.

2.3 Study Phase, Visit, and Day

The study is set up as shown above, along with study phase, visit, and day. In general, the baseline is defined as the last assessment before the first intake of the study medication unless otherwise specified. All scheduled assessments after first administration of study drug will be used.

Repeat/unscheduled assessments will not be used in descriptive statistics or any per-time point analyses but will be shown in listings as applicable. Pre-dose unscheduled assessments will be taken into account for baseline determination and post first dose unscheduled assessments will be taken into account for worst-case determination as applicable.

Reference date refers to the start date of the first study drug administration. All efficacy and safety assessments at all visits will be assigned a day relative to this date. The relative day will be defined as: visit date – reference date + 1 for visits on or after the reference date and visit date – reference date for visits before the reference date. Consequently, there is no 'Day 0' defined.

2.4 Analysis Datasets

- Screened Dataset (SCRN): All subjects who were screened and entered into EDC.
- Screen Failure Dataset (SCRF): All subjects who were entered as screen failures in the EDC.
- Intention-to-Treat Dataset (ITT): All randomized subjects.

- Safety Dataset (SAF): All subjects who received at least one dose of the study agent.
- Evaluable Dataset (EVAL): All subjects who receive at least 4 of the 5 planned doses.
- Per Protocol Dataset (PPROT): A subset of the Evaluable Dataset comprised of subjects who do not have any of the deviations listed below or any other deviation affecting efficacy identified prior to database lock.

Deviation Type	Deviation	Additional Clarification
Eligibility Inclusion Criteria Not Met	Diagnosis of AD based upon the National Institute on Aging-Alzheimer's Association (NIA-AA) Criteria	
Eligibility Inclusion Criteria Not Met	MMSE Score 0-10 inclusive	
Eligibility Inclusion Criteria Not Met	Modified Hachinski Ischemia Scale (MHIS) score of <=4	
Eligibility Inclusion Criteria Not Met	If on medications for cognition (e.g., rivastigmine, galantamine, donepezil, memantine), must be on stable dosage for at least 8 weeks prior to Baseline	Will be dependent upon timing of dose change
Eligibility Inclusion Criteria Not Met	If on daily antidepressant medications and/or benzodiazepines and/or typical or atypical antipsychotics, must be on stable dosage for 8 weeks prior to Baseline. If on prn dosing with atypical antipsychotics and/or benzodiazepines, these should not be given within 24 hours before each day of cognitive and other ratings (V1, V2, V8, V9, V10)	Will be dependent upon timing of dose change
Eligibility Exclusion Criteria Met	Evidence of clinically relevant neurological disorder(s) other than AD	
Eligibility Exclusion Criteria Met	Treatment with any human blood product, including transfusions and IV immunoglobulin, during the 6 months prior to screening	

Deviation Type	Deviation	Additional Clarification
Eligibility Exclusion Criteria Met	Concurrent participation in any other therapeutic treatment trial. If there was prior clinical trial participation, subject must have discontinued investigational agents for at least 30 days for small molecules, and 1 year for active or passive immunotherapies prior to Screening	
Eligibility Exclusion Criteria Met	Subjects who have a level of agitation that, in the opinion of the investigator, could interfere with study procedures	
Eligibility Exclusion Criteria Met	Any other condition and/or situation that the investigator believes may interfere with the safety of the subject, the intent and conduct of the study, or interpretation of study data	Only when interfering with the interpretation of study data
Compliance	Incorrect treatment dispensed and administered to subject	
Out of Window	Efficacy Procedures performed outside of the protocol window which are a consistent pattern or potential risk to study data outcomes	
Study Drug Temp Excursion	Study drug temperature excursions when determined to have impacted the quality of the study drug	
Concomitant meds	Use of prohibited concomitant medications as defined in the protocol that have an effect on cognition	

Decisions regarding which subjects are included in the PPROT will be made before database lock.

A summary table of number (%) of subjects in each analysis set and applicable treatment assignment will be provided (Table 14.1.1).

The presentation of baseline characteristics will be conducted on the ITT dataset. All safety analyses will be performed for the SAF dataset. Analyses of the secondary endpoints will focus on the EVAL and/or PPROT datasets.

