2.3 POTENTIAL RISKS AND BENEFITS

2.3.1 KNOWN POTENTIAL RISKS

Collected human plasma may be used as a therapeutic product (known as “plasma” or “fresh frozen plasma”) or as source material for the production of pharmaceutical fractionated products (known as “plasma products” or “plasma derivatives”) (Burnouf 2007). GRF6019, a [REDACTED] human plasma protein fraction, [REDACTED] serves as a viable source of soluble, infusible plasma proteins from [REDACTED] healthy donors. [REDACTED]

[REDACTED] ABO antigen typing is not required prior to administration. Finally, the additional steps taken during production to remove viral pathogens provide an increased margin of pathogen safety in comparison to fresh frozen plasma.

[REDACTED] GRF6019 is not expected to significantly alter the urinalyses of recipients, their bleeding times, coagulation times, prothrombin times, prothrombin consumption, platelet counts or fibrinogen levels when given in quantities of up to 1000 mL. Decreased blood pressure may occur, particularly following rapid infusion. The blood pressure may normalize spontaneously after the slowing or discontinuation of the infusion. [REDACTED]

GRF6019 is made from human plasma and may carry a risk of transmitting infectious agents, e.g., viruses, the variant Creutzfeldt-Jakob disease (vCJD) agent, and, theoretically, the Creutzfeldt-Jakob disease (CJD) agent. The risk that GRF6019 can transmit an infectious agent has been reduced by screening plasma donors for prior exposure, testing donated plasma, and including manufacturing steps with the capacity to inactivate and/or remove pathogens.

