4.2 STUDY ENDPOINTS

4.2.1 PRIMARY ENDPOINTS

The primary endpoints pertain to safety and tolerability of the GRF6019 dosing regimen in subjects with severe AD.

The primary safety endpoint is as follows:

- Incidence of treatment-emergent adverse events (AEs) and serious adverse events (SAEs) identified by MedDRA PT and grouped by MedDRA SOC.

Tolerability endpoint is as follows:

- Number of subjects completing 4 weeks after receiving at least 5 infusions.

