4.6 Extent of Exposure

The extent of exposure (days) is defined as date of last study drug intake – date of first study drug intake + 1 within the dosing period. For subjects that have a “grace day” (i.e. they received 5 infusions over a period of 6 days instead of 5 infusions over 5 consecutive days), such dosing “grace day” is not considered an interruption. Extent of exposure as well as actual volume administered will be summarized descriptively overall (Table 14.1.7.1).

Descriptive statistics of actual infusion rate (mL/hour) will be summarized at each time point per infusion day (Table 14.1.7.2). The numbers of below, within and above the designated infusion rate reference will be tabulated at each time point per infusion day (Table 14.1.7.3). In addition, descriptive statistics or frequency tabulation will be provided for the following infusion parameters collected at each infusion day (Table 14.1.7.4):

- Required adjustment to flow rate (Yes, No)
- Entire assigned dose administered (Yes, No)
- Actual Volume Administered (mL)
- Maximum flow rate (mL/hour)
- Volume of Saline Flush
- Device used to administer infusion (Baxter Flo Gard, Other)

Unscheduled changes in flow rate will be included in the subject data listing only

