4.7 Treatment Completion

Treatment completion is calculated as the actual volume administered, as a percentage of the volume expected. The expected dose overall will be calculated

as [5 x total daily dose volume] for all subjects, regardless of study completion status. Treatment completion will be summarized descriptively and categorically (<75% and >=75%) overall (Table 14.1.8.1).

In addition, number of subjects completing 1, 2, 3, 4, and 5 infusions will be summarized (Table 14.1.8.2).

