4.8 Tolerability

Number of subjects completing 4 weeks after receiving at least 5 infusions will be tabulated (Table 14.1.9).

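### Does the missing rule for partly given infusions leave the Evaluable Dataset and the tolerability count undefined?

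*SAP*

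**What the plan says.** Two counts depend on the number of infusions a subject had.

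- **Evaluable Dataset.** SAP 2.4: "Evaluable Dataset (EVAL): All subjects who receive at least 4 of the 5 planned doses". Protocol 10.3 has the same definition. The Per Protocol Dataset is a subset, and Tables 14.2.1 to 14.2.5 use both sets.
- **Tolerability.** Protocol 4.2.1: "Number of subjects completing 4 weeks after receiving at least 5 infusions". SAP 4.8 repeats this and sends it to Table 14.1.9. Only five infusions are planned, so the threshold means all of them.

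The plan foresees infusions that do not run to the end. On a fall in blood pressure, Protocol 2.3.1 says: "The blood pressure may normalize spontaneously after the slowing or discontinuation of the infusion". For each infusion day SAP 4.6 records the volume given and a yes/no item, "Entire assigned dose administered (Yes, No").

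Other passages measure dosing in other ways. SAP 4.6 defines extent of exposure as "date of last study drug intake – date of first study drug intake + 1". SAP 4.7 cuts volume at 75%: "Treatment completion will be summarized descriptively and categorically (<75% and >=75%) overall (Table 14.1.8.1"). It also says that the "number of subjects completing 1, 2, 3, 4, and 5 infusions will be summarized (Table 14.1.8.2"). Protocol 6.1.8 sets evaluability at four exposure days and ties it to the intent-to-treat population. Protocol 5.4.2 uses the word evaluable for its enrolment target of about 16, meaning five doses and completion of Visit 8.

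**The concern.** Neither document says in terms whether a started but unfinished infusion is a dose or infusion received, so two analysts could assign a subject differently. The affected subjects are unlikely to be a random subset, because an infusion may be cut short for an adverse event. On the any-amount reading, a subject whose five infusions were each stopped halfway could count as having tolerated the full course. On the whole-infusion reading the same subject fails tolerability and drops out of the Evaluable and Per Protocol Datasets. Tolerability is part of the primary objective, and this count sits under Primary Endpoints in Protocol 4.2.1.

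The scatter of terms (doses, infusions, exposure days, percentage of volume, calendar span) also suggests that the documents disagree about the unit. SAP 8, which lists changes from the protocol, settles none of this.

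**Working it through.** **The plan's own figures.** The Protocol Summary assumes 20 enrolled and 20% drop-out: 20 × (1 − 0.20) = 16, as stated. The full course (Protocol 6.1.7) is 5 × 250 = 1250 mL. Four whole infusions are 1000 mL (1000/1250 = 80%). The 75% cut is 0.75 × 1250 = 937.5 mL.

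**Is there a conflict of units?** Protocol 6.1.7 gives one infusion per day, and the Schedule of Events numbers infusions 1 to 5 on Days 1 to 5. Protocol 6.1.8 moves directly from five days of therapy to five exposure days. Four exposure days are therefore four doses, which is the Evaluable threshold.

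A conflict appears only if the SAP 4.6 formula is read into 6.1.8:

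- Infusions on Days 1 and 4 only: 4 − 1 + 1 = 4 days from 2 doses.
- Five infusions with the permitted grace day: 6 − 1 + 1 = 6 days from 5 doses.

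That formula is the SAP's summary for Table 14.1.7.1. No passage uses it for the Evaluable Dataset.

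**What the partial-infusion question changes.** The volumes below are assumed, since the documents give no rate of incomplete infusions. The tolerability columns show only whether the five-infusion condition is met.

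| Pattern | Total (mL) | % of 1250 | Evaluable: any amount | Evaluable: whole only | Five infusions: any amount | Five infusions: whole only |
|---|---|---|---|---|---|---|
| 5 × 125 | 625 | 50.0 | yes | no | yes | no |
| 5 × 190 | 950 | 76.0 | yes | no | yes | no |
| 3 × 250 + 190 | 940 | 75.2 | yes | no | no | no |
| 4 × 230 | 920 | 73.6 | yes | no | no | no |
| 4 × 250 + 100 | 1100 | 88.0 | yes | yes | yes | no |
| 5 × 250 | 1250 | 100.0 | yes | yes | yes | yes |

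The readings do differ for partial infusions. Rows two to four also show subjects on either side of the 75% cut with the same Evaluable status. That is two measures answering different questions, not a contradiction.

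**Size of one reclassification.** At 2:1, 20 subjects split 13 and 7 or 14 and 6. One subject is 1/14 = 7.1% or 1/13 = 7.7% of the active arm, and 1/7 = 14.3% or 1/6 = 16.7% of the placebo arm.

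**Which way the text leans.** The Safety and Evaluable Datasets stand in one list in SAP 2.4 and share the same verb and noun, dose received. For the Safety Dataset any amount is the natural reading, because Protocol 8.4.1 assesses causality once an infusion has been initiated. SAP 4.7 speaks of completing infusions, and SAP 4.8, directly after it, of receiving them. The change of verb suggests that received is the weaker condition.

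**What the reader will see.**

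- Table 14.1.7.4: whether the entire dose was given, and the volume, per infusion day.
- Tables 14.1.8.1 and 14.1.8.2: percentage of volume, and infusions completed.
- Listings 16.2.1.1, 16.2.5.5, 16.2.5.6 and 16.2.5.7: analysis-set membership, daily infusion record, treatment completion and tolerability, by subject.
- Listings 16.2.6.1 to 16.2.6.5: efficacy data on all randomized subjects, so leaving the Evaluable Dataset hides nobody's scores.

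**The case for a change.** The best argument for a change is that this is the plan's only designated tolerability endpoint, that a stopped infusion is itself a tolerability finding, and that a sentence in the SAP costs almost nothing. SAP 2.4 also requires membership decisions before database lock for the Per Protocol Dataset only.

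Part of this stands. The counting rule is unstated, and the any-amount reading is the more flattering one for tolerability. The Infusion Administration Manual is not among the documents, and neither definition refers to it for counting.

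The rest carries less weight. The proposed remedy asks the sponsor to choose a rule but does not show that one rule is better, and no rule now in the plan gives a wrong result. A second row in Table 14.1.9 would add little to what the infusion tables and listings give for some 20 subjects. Adverse events that lead to holding or stopping treatment are recorded as such, so repeated stopping for an adverse event would not pass unseen behind a favourable count. The lock argument is weaker than it looks for the Evaluable Dataset: because the Per Protocol Dataset is a subset of it, a subject with a partial infusion and no excluding deviation cannot be placed in or out of the Per Protocol Dataset until Evaluable status is settled.

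The other uses of evaluable are loose wording. The link to intent-to-treat in Protocol 6.1.8 is a slip, since both documents define that set as all randomized subjects. Protocol 5.4.2 sets an enrolment and replacement target and does not define an analysis set.

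**Conclusion.** No change is needed. The charge of mixed units does not hold: with one infusion a day the units coincide, and the volume and calendar-span measures belong to other tables. What remains is an unstated detail about partial infusions. The text leans towards counting any administered amount, and analysts can apply that reading without contradicting any definition.

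The effect is nil if every infusion is completed. Otherwise it is one subject at a time: 7.1 to 7.7 points on GRF6019 or 14.3 to 16.7 on placebo, for an endpoint that the plan states as a number of subjects. Efficacy is descriptive and unpowered, and the adverse event tables do not move if any amount counts for the Safety Dataset.

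This rests on two assumptions: that incomplete infusions are few, on which the documents give no figure, and that the planned infusion tables and subject listings are produced, so that a reader can match each partial infusion to that subject's status.

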2.5 Definition of Subgroups

Not applicable.

2.6 Descriptive Summaries

All tabulated summaries will include the two treatment groups and overall (includes data from both treatment groups). For endpoints that are continuous in nature: number of observations, mean, standard error of the mean (SEM),

median, minimum and maximum, and standard deviation (SD) values will be presented as descriptive summary. For endpoints that are categorical in nature: frequency counts and percentages will be presented in the descriptive summary.

The number of decimal places to display for calculated data will be determined by the original scale of the data. Means, medians, and confidence intervals will be reported with one (1) additional decimal place. Standard deviation will be reported with two (2) additional decimal places. Minimum and maximum will be reported with the same number of significant digits as the method of capture.

For all efficacy and safety tables summarizing change from baseline, the baseline and post-baseline results at all planned timepoints will be included.

3 PLANNED INTERIM ANALYSIS

No interim analyses of efficacy data are planned. Safety data will be assessed in an ongoing manner.

4 SUBJECT INFORMATION

In general, all subject-level parameters will be summarized for the SAF set unless stated otherwise.

4.1 Disposition Information

Summaries will be provided for the following disposition information: Number of subjects screened, screening failures, randomized, randomized not treated, completed study, discontinued from study drug with the reasons of discontinuation from study drug, and discontinued from study but completed study drug dosing with the reasons of discontinuation. The SCRN set will be used for the subject disposition table (Table 14.1.2).

4.2 Protocol Deviations

The number and percentage of subjects with protocol deviations will be tabulated per coded protocol deviation by severity (major vs minor) for the ITT set (Table 14.1.3.1).

The success of blinding will be assessed based on all occurrences (intentional or unintentional) of unblinding of blinded study subjects, their caregivers or study personnel (e.g. investigators, medical providers, cognitive testing raters, the Sponsor or their representatives) during infusions. Number of subjects with any occurrence of unblinding will be summarized on any day during treatment phase, each day during treatment phase within the study, and any day during the study (Table 14.1.3.2).

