4.2.2 SECONDARY ENDPOINTS

This study is not powered to detect statistically significant differences in cognitive domains between the baseline and end of study values. Secondary endpoints will be summarized over the study period from baseline values using descriptive statistics.

Secondary safety endpoints are as follows:

- Changes from baseline in clinical laboratory parameters.
- Changes from baseline in vital sign measurements.
- Changes in body weight from baseline to Visit 8.
- Changes from baseline in physical exam parameters at Visit 10 or End of Study/Early Termination.
- Changes from baseline in ECG recordings.

Secondary efficacy endpoints are as follows:

- Changes in the MMSE ([Folstein 1975, Appendix 1](#)).
- Changes in the SIB ([Paniiset 1994, Appendix 2](#)).
- Changes in the ADCS-ADL-Severe ([Galasko 2005, Appendix 3](#)).
- Changes in the ADCS-CGIC ([Ferris 1997, Schneider 1997, Appendix 4](#)).
- Change on the NPI/NPI-NH ([Cummings 1994, Wood 2000, Appendix 5](#)).

Secondary feasibility endpoints include:

- Subject compliance with the study visit schedule, procedures, infusions, and any required adaptations that are necessary for study completion.
- Success of blinding. This will be assessed based on all occurrences (intentional or unintentional) of unblinding of blinded study subjects or study personnel (e.g. investigators, medical providers, cognitive testing raters, the Sponsor or their representatives).

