5.4.2 HANDLING OF PARTICPANT WITHDRAWALS OR TERMINATION

Subjects will be encouraged to complete the study and all assessments. However, subjects may voluntarily withdraw at any time, and the investigator may discontinue individual subjects from the study at any time.

Approximately 20 subjects will be enrolled in the study with the intent of obtaining ~16 evaluable subjects who have received at least 5 doses and completed through Visit 8. Subjects who discontinue or are unblinded prior to completing Visit 8 may be replaced. Subjects who withdraw or are withdrawn during Screening will be replaced.

Subjects who have received at least one infusion but are withdrawn or withdraw from the study will be encouraged to complete the End of Study procedures within approximately 4 weeks of their last visit. For post-study AE and SAE reporting, see [Section 8.3.1](#). The primary reason for study discontinuation will be documented on the case report form (CRF).

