10.6.2 EVALUATION OF SUCCESS OF BLINDING

Success of blinding will be assessed based on all occurrences (intentional or unintentional) of unblinding of blinded study subjects or study personnel (e.g. investigators, medical providers, cognitive testing raters, the Sponsor or their representatives). All intentional and unintentional unblinding will be documented and reported.

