10.6.3 BREAKING THE STUDY BLIND/SUBJECT CODE

The study blind may be broken for safety reasons if the information is required for the management of SAEs or severe AEs or if the investigator believes that the safety of the subject is at stake and that unblinding is necessary. Any noted intentional or unintentional breaking of the blind should be reported to the Sponsor or

their representatives. If unintentional unblinding occurs during the study, root cause analysis will be evaluated, and corrective actions implemented as appropriate.

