1.4 Randomization and Blinding

To minimize the potential bias at the time of randomization, the study will be double-blind and randomized with a 2:1 ratio to GRF6019 (Group 1) or placebo (Group 2). A stratified block randomization will be implemented by sex. The randomization codes will be generated by a statistician who has no involvement in the study other than generation and maintenance of the randomization codes.

All study outcome measures will be assessed by blinded Outcomes Assessors or other blinded raters. However, [REDACTED] GRF6019 or placebo will be dispensed by an unblinded pharmacist, or other qualified staff responsible for drug accountability, to an unblinded Infusion Nurse who will administer the infusion. To ensure that Outcomes Assessors, raters, and other study personnel as well as subjects and their caregivers are unaware of the allocation, appropriate measures will be taken to mask the study agent/placebo containers and IV setup such that they will only be visible as necessary to the unblinded Infusion Nurse. In addition, a curtain, drape, or equivalent may be used to shield the infusion administration setup from view of all but the unblinded Infusion Nurse, and the unblinded Infusion Nurse will be responsible for concealing and returning used containers of the study agent or placebo to the pharmacy at the end of the Infusion Period. The unblinded Infusion Nurse will

enter the infusion data and blinding assessment into the eCRF to avoid unblinding of the source data during data entry.

During the infusion, communication between the blinded Outcomes Assessor and the unblinded Infusion Nurse should be limited to only that required to ensure the immediate safety of subjects. The Outcomes Assessors will observe the subject during the infusion and collect and/or manage/report AEs and SAEs.

Except for the unblinded CRA(s) whose sole responsibility is to ensure the study agent/placebo is being dispensed, administered, and disposed of properly, the study Sponsor and their representatives will be blinded with respect to the infusion product.

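### SAP 4.2 narrows the success-of-blinding endpoint to unblinding during infusions, against the protocol and against its own table, and names no data source for later breaks

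*SAP*

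**What the plan says.** Protocol 4.2.2 makes this a secondary feasibility endpoint: "Success of blinding. This will be assessed based on all occurrences (intentional or unintentional) of unblinding of blinded study subjects or study personnel". Protocol 10.6.2 repeats the definition and adds: "All intentional and unintentional unblinding will be documented and reported". Protocol 10.6.3 allows the blind to be broken for safety and gives the reporting route: "Any noted intentional or unintentional breaking of the blind should be reported to the Sponsor or" its representatives. None of the three sections sets a time window.

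SAP 4.2 uses nearly the same definition and adds caregivers, which is a widening. It then closes the list of people with "e.g. investigators, medical providers, cognitive testing raters, the Sponsor or their representatives) during infusions". Its next sentence tabulates subjects with any unblinding on any treatment day, "each day during treatment phase within the study, and any day during the study (Table 14.1.3.2").

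On data entry, SAP 1.4 says the unblinded Infusion Nurse will "enter the infusion data and blinding assessment into the eCRF to avoid unblinding of the source data during data entry".

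On data handling, protocol 5.4.2 says: "Subjects who discontinue or are unblinded prior to completing Visit 8 may be replaced". In SAP 2.4, EVAL is defined by dose count alone (at least 4 of 5). PPROT is a subset of EVAL "comprised of subjects who do not have any of the deviations listed below or any other deviation affecting efficacy identified prior to database lock". Unblinding is not among the listed deviations.

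SAP 8 (Changes from Protocol) covers the PPROT definition and the blood pressure ranges only.

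**The concern.** A protocol-named endpoint has a narrower definition in the SAP, and the change is not declared. The part left out is the part that bears most directly on the efficacy ratings: the weeks after dosing, when raters and informants are interviewed. ADCS-CGIC is a clinician's judgement that draws on informant interviews, and ADCS-ADL-Severe and NPI/NPI-NH are informant-reported, so knowledge of allocation can colour all three.

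A code break made to manage a serious event during follow-up, or a disclosure to a rater or caregiver after Day 5, could be missing from the table meant to show whether the blind held. A reader of the study report could not tell a table with no late breaks from a table that never looked for them.

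**Working it through.** The plan gives no figure to reproduce. The check is a comparison of text plus a count of visits.

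**1. Definition.** Protocol 4.2.2 and 10.6.2: all occurrences, any time. SAP 4.2, definition sentence: occurrences during infusions. SAP 8: silent. The two documents differ and the difference is undeclared.

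**2. Internal consistency of SAP 4.2.** Let T be the subjects with a counted break on any treatment-phase day, and S those with a counted break on any study day. If only breaks during infusions count, every counted break falls in the treatment phase, so S = T for any data and the third row carries no information. If S is to differ from T, breaks outside infusions must count, and the definition sentence is wrong. Two programmers could build Table 14.1.3.2 differently and each point to SAP 4.2.

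**3. Timing.**
- Infusions: Visits 3 to 7, nominal Days 1 to 5 (protocol 7.3.4). With the permitted grace day, the fifth can fall on Day 6.
- Scheduled post-dose ratings: Days 6, 12 and 33, that is Visits 8, 9 and 10 (SAP 5.1 to 5.5). Visit 8 follows the last infusion and may be up to 3 days later than Day 6 (protocol 7.3.5).
- Overlap of {1, 2, 3, 4, 5} with {6, 12, 33}: none.
- Efficacy summaries under the SAP: MMSE 2 + SIB 3 + ADCS-ADL-Severe 1 + ADCS-CGIC 3 + NPI/NPI-NH 2 = 11, all on those three days.
- Nominal study days after the last infusion: 33 − 5 = 28 of 33, or 28/33 = 85%, before the ±7-day window at Visit 10.

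On the literal reading, a break first arising in those 28 days is not counted. The period between randomization and the first infusion is also outside, since protocol 7.3.3 lets randomization precede Visit 3.

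**4. Data source.** The SAP names one input for the blinding assessment, the nurse's entry made with the infusion data (SAP 1.4). SAP 1.5 describes the study data as eCRF and safety laboratory data. Breaks reported to the sponsor under protocol 10.6.3, and the deviation log under protocol 13.3, should exist, but the SAP does not say that they feed Table 14.1.3.2. Even on the wide reading, the any-day row has no stated input after dosing.

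**5. Ratings made after a break.**
- EVAL: dose count only, so the ratings stay.
- PPROT: not listed by name. Protocol 10.6.1 and SAP 1.4 require outcome measures to be assessed by blinded raters. A rating by an unblinded rater therefore departs from protocol and is a deviation under protocol 13.3. The PPROT catch-all and the pre-lock review in SAP 8 can reach it, at the team's discretion. The position of an unblinded informant is less clear.

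**The case against.** The best defence is that SAP 4.2 is ambiguous, not restrictive. SAP 1 says the SAP is read together with the protocol, the protocol counts all occurrences, and the any-day row has meaning only if later breaks are included. That stands to this extent: a reader might infer that later breaks are definitely excluded and that the table would report none, but the documents do not establish this. They support a contradiction that must be resolved, with the narrow reading as one outcome.

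Three other inferences are also too strong:
- **That no break affecting the rating visits is counted.** A rater or caregiver unblinded during an infusion presumably remains so at Visits 8 to 10, and that break is counted on any reading. Much of the masking effort concerns the infusion setup. Only breaks first arising outside infusions are in doubt.
- **That an unblinded person's ratings stay in both efficacy sets.** This is certain for EVAL only, because the PPROT catch-all can remove them. The replacement option in protocol 5.4.2 is an enrolment rule and says nothing about a subject's data.
- **That the nurse's entry is the only record.** It is the only source the SAP names. The protocol requires all breaks to be documented and reported.

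Efficacy is secondary, unpowered and descriptive, so no hypothesis test is affected. With about 16 evaluable subjects at 2:1, the placebo arm is 16/3 ≈ 5.3, so one subject would be roughly a fifth of it. That shows how small the arm is. Neither document gives a rate of unblinding or a number of subjects per rater, so it is not an estimate of harm.

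**Conclusion.** The point holds as a defect of definition and data source. SAP 4.2 conflicts with protocol 4.2.2 and 10.6.2 and with its own tabulation, and SAP 8 does not say so. Read literally, it leaves out breaks first arising over 28 of the 33 nominal study days, the period that holds all three scheduled post-dose rating visits and all 11 efficacy summaries.

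This rests on nominal visit days and on the literal meaning of the definition sentence. How many breaks would be missed is unknown, and it may be none. The documents do not show that data are lost, or that unblinded ratings are certain to remain in PPROT. The correction is worth making before database lock because the rule is wrong as written and cheap to repair.

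**What to change.** 1. **SAP 4.2:** delete the words *during infusions*, so that the definition matches the protocol and the any-day row has content.
2. **Table 14.1.3.2:** count, by arm, every break from randomization to Visit 10. Name the sources: the infusion-day blinding form, code breaks reported to the sponsor, and the deviation log. Show who was unblinded (subject, caregiver, rater, investigator, other) and whether the break preceded each of Visits 8, 9 and 10.
3. **Listings 16.2.6.1 to 16.2.6.5:** flag ratings made after the subject, rater or informant was unblinded. State in SAP 2.4 that EVAL keeps them and that PPROT reaches them only through its existing catch-all.
4. **SAP 8:** record any remaining difference from the protocol, including the addition of caregivers.

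A visit-level PPROT exclusion is not recommended. Code breaks under protocol 10.6.3 follow serious or severe events or a threat to the subject's safety, so dropping later ratings would be informative removal in a very small arm. Flagging lets the reader judge.

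Cost: SAP wording, one revised table and a listing flag. No new collection should be needed, since the protocol already requires breaks to be documented and reported. This assumes that those reports give the date and the person unblinded; if they do not, these details must be obtained before lock.
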